3.4 Additional Efficacy Endpoints

All secondary endpoints will be analyzed at all visits other than those listed. In addition, the following endpoints will be analyzed at all visits assessed, per [Appendix F](#):

- Time to disease flare defined as Polymyalgia Rheumatica Activity Score (PMR-AS) increased from Baseline by ≥ 6.6 .
 - $\text{PMR-AS} = \text{high-sensitivity CRP (hsCRP) (mg/dL)} + \text{Patient Assessment of Pain Severity (numeric rating scale [NRS], 0 – 10)} + \text{Physician Global Assessment of Disease Activity (NRS, 0 – 10)} + (\text{morning stiffness duration [MST] in minutes} \times 0.1) + \text{elevation of upper limbs (EUL) (scale of 3 – 0)}$
- Time to disease flare defined as $\text{PMR-AS} \geq 9.35$
- Achievement of $\text{PMR-AS} < 1.5$
- Achievement of $\text{PMR-AS} < 7$
- Achievement of $\text{ESR} \leq 30 \text{ mm/h}$ at Week 24
- Achievement of $\text{hsCRP} \leq \text{upper limit of normal (ULN)}$ at Week 24
- Change from Baseline in hsCRP
- Change from Baseline in PMR-AS
- Change from Baseline in MST
- Change from Baseline in EUL
- Change from Baseline in Physician Global Assessment of Disease Activity NRS
- Change from Baseline in Patient Assessment of Pain Severity NRS
- Change from Baseline in Patient Assessment of Stiffness Severity NRS
- Change from Baseline in Functional Assessment of Chronic Illness Therapy-Fatigue (FACIT-Fatigue)
- Change from Baseline in Health Assessment Questionnaire Disability Index (HAQ-DI)
- Change from Baseline in Patient-Reported Outcomes Measurement Information System (PROMIS) Item Bank v 1.0 – Sleep Disturbance
- Change from Baseline in Patient Assessment of Bruising Severity NRS
- Change from Baseline in EuroQoL 5-dimension questionnaire, 5-level (EQ-5D-5L)
- Change from Baseline in Physician Assessment of Bruising Severity NRS
- For subjects participating in the Wearable Device Substudy:
 - Change from Baseline in the following sleep parameters: total sleep time, wake after sleep onset, sleep efficiency, and sleep onset latency
 - Change from Baseline in upper limbs range of motion (UL-ROM)

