- ✓ 8. Subject must have had at least 2 episodes of unequivocal PMR flare while attempting to taper prednisone, with the dose of prednisone (or equivalent) at the time of flare ≥ 5 mg/day, prior to Baseline; the most recent flare must have been within 24 weeks of Baseline. Unequivocal PMR flare is defined as clinical signs and symptoms of PMR (shoulder and/or hip girdle pain with inflammatory stiffness, neck pain with inflammatory stiffness, or new or worsened limited range of motion of hips and/or shoulders) that resulted in an increase in glucocorticoid dose.

- ✓ 9. Subject must not exhibit clinical signs and symptoms of PMR (shoulder and/or hip girdle pain with inflammatory stiffness, neck pain with inflammatory stiffness, or new or worsened limited range of motion of hips and/or shoulders) within 2 weeks of Baseline.

Subject History

- ✓ 10. Subject is judged to be in good health as determined by the Principal Investigator, based upon the results of medical history, laboratory profile, physical examination, chest x-ray (CXR), and a 12-lead ECG performed during Screening.
- ✓ 11. No history of an allergic reaction or significant sensitivity to constituents of the study drug (and its excipients) and/or other products in the same class. No history of anaphylactic reaction to any agent (e.g., food products and bee sting); or a reaction to any immunoglobulin G (IgG) containing product.
- ✓ 12. Subject must have no current or past history of infection including:
 - Active tuberculosis (TB) or meets TB exclusionary parameters (specific requirements for TB testing are provided in the Operations Manual);
 - Subjects **in Japan** only: Positive result of beta-D-glucan (screening for *Pneumocystis jirovecii* infection) or two consecutive indeterminate results of beta-D-glucan during the Screening Period.
 - Human Immunodeficiency virus (HIV) infection defined as confirmed positive anti-HIV antibody (HIV Ab) test;
 - Active infection(s) requiring treatment with intravenous anti-infectives within 30 days, or oral/intramuscular anti-infectives within 14 days prior to the first dose of study drug;
 - Chronic recurring infection and/or active viral infection that, based on the investigator's clinical assessment, makes the subject an unsuitable candidate for the study;

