7.4 Statistical Analyses for Efficacy

Efficacy analysis will be performed by the subject's randomized treatment group. All statistical tests will be performed at a 2-sided significance level of 0.1. A 95% confidence interval (CI) of the treatment difference between each ABBV-154 dose and placebo will be provided. The actual value of stratification factors will be used in the analysis. Enrollment in the optional PK sampling is not expected to impact any of the efficacy endpoints and will thus not be used as a stratification factor in the analysis.

- For time-to-event endpoints, comparison of number of events will be made between each ABBV-154 dose and placebo based on log-rank test stratified by stratification factors. The point and CI estimate of median time to event and event-free rate for each group will be reported based on Kaplan-Meier curves. Hazard ratio and its corresponding CI for each ABBV-154 group compared with placebo will be estimated using Cox regression analysis adjusting for stratification factors. For all analyses of time-to-event endpoints, subject without an event at the time of the analysis will be administratively censored at the time of the last available assessment.
- For categorical variables, pairwise comparison will be made between each ABBV-154 dose and placebo using the Cochran-Mantel-Haenszel (CMH) test, adjusting for stratification factors. Nonresponder imputation incorporating multiple imputation (NRI-MI) to handle COVID-19 will be the primary approach to handle missing data for categorical endpoints.
- For continuous variables other than glucocorticoid dose, the comparison will be made between each ABBV-154 dose and placebo based on the mixed effect model repeated measures (MMRM) adjusting for visit, interaction between treatment and visit, actual values of stratification factors as fixed factors, and baseline value as a covariate. The MMRM will be the primary approach to handle missing values for continuous endpoints.
- For analyses of glucocorticoid dose, comparison will be made between each ABBV-154 dose and placebo based on the analysis of covariance (ANCOVA) adjusting for stratification factors as fixed factors, and baseline glucocorticoid dose as a covariate.

Summary and Analysis of the Primary Endpoints

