## 9.2.2 Handling of Intercurrent Events and Missing Data in Categorical and Continuous Endpoints

- Non-Responder Imputation incorporating multiple imputation to handle COVID-19 (NRI-MI) will be the primary approach to handle missing data for categorical endpoints. The NRI-MI will categorize any subject who does not have an evaluation during a pre-specified visit window (either due to missing assessment, due to early withdrawal from the study, or due to intercurrent event) as a non-responder for the visit. The only exceptions are: 1) when the subject is a responder both before and after the visit window, the subject will be categorized as a responder for the visit. 2) missing data due to COVID-19 infection or logistical restriction will be handled by Multiple Imputation. In addition, all assessments after the start of intercurrent events will not be included in the analyses; as a result, subjects will be counted as non-responders thereafter and will not be imputed by MI.
- Non-Responder Imputation (NRI): In the interim analyses, NRI may be used due to subjects being in the study for different durations which makes multiple imputation infeasible.
- Multiple Imputation (MI): Markov Chain Monte Carlo (MCMC) will be first applied to augment data into monotonic missing pattern and PROC MI will be used to generate 30 datasets using the regression method. The variables to be included in the imputation model are treatment group, stratification factors at randomization [Glucocorticoid use at Baseline ( $\geq 10$  mg/day;  $< 10$  mg/day prednisone equivalent); Length of prior glucocorticoid treatment for PMR ( $\leq 1$  year;  $> 1$  year)], Baseline, and measurements at each visit. The random seed for MCMC and the random seed for PROC MI are specified in Appendix C. The imputed post-baseline measurements will be rounded to the same precision as the observed data before the determination of responder status. Subjects will be characterized as responders or non-responders based on MI imputed datasets. Using the Cochran-Mantel-Haenszel (CMH) model adjusted by stratification factors [Glucocorticoid use at Baseline ( $\geq 10$  mg/day;  $< 10$  mg/day prednisone equivalent); Length of prior glucocorticoid treatment for PMR ( $\leq 1$  year;  $> 1$  year)], the imputed endpoints will be analyzed using each of the 30 datasets. SAS PROC MIANALYZE will be used to generate the final inferences of the risk difference between each ABBV-154 group and

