## 9.5 Additional Efficacy Analyses

Additional efficacy endpoints described in Section 3.3 will be analyzed at all visits assessed using the same methods listed in above and Section 9.2. The attributes of the estimands corresponding to the additional efficacy endpoints are summarized in Table 3.

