**Table 3. Summary of the Estimand Attributes of the Additional Efficacy Endpoints**

For binary endpoint:

Estimand Label	Attributes of the Estimand				
	Treatment	Endpoint	Population	Handling of Intercurrent Events	Statistical Summary
Binary Additional Variable (Composite)	ABBV-154 vs. Placebo	Achievement of each binary additional endpoint respectively	ITT	IE1: Initiation of rescue medication IE2: Initiation of immunomodulator IE3: Initiation of violation of protocol-allowed systemic glucocorticoid use  Subjects will be considered as non-responders for visits after ICEs.	Difference in proportion of subjects achieving each binary additional endpoint

For continuous endpoint:

Estimand Label	Attributes of the Estimand				Statistical Summary
	Treatment	Endpoint	Population	Handling of Intercurrent Events	
Continuous Additional Variable (Composite)	ABBV-154 vs. Placebo	Change from Baseline in each respective continuous additional endpoint	ITT	IE1: Initiation of rescue medication IE2: Initiation of immunomodulator IE3: Initiation of violation of protocol-allowed systemic glucocorticoid use  Efficacy assessments after the start of IE will not be included in the analyses, and visits after IE will be handled by MMRM.	Difference in the mean change from Baseline in each continuous additional endpoint

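### The threshold endpoints for ESR, hsCRP and PMR-AS are compared without adjusting for Baseline, which costs some precision and lets chance imbalance shift the estimate

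*Protocol*

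**What the plan says.** **Endpoints.** Protocol Section 3.4 and SAP Section 3.3 list four threshold endpoints: ESR ≤ 30 mm/h, hsCRP no higher than the "upper limit of normal (ULN"), PMR-AS < 1.5 and PMR-AS < 7. Each depends only on the value at the visit. SAP Table 3 gives the endpoint as "Achievement of each binary additional endpoint respectively", in the ITT Population, with no condition on Baseline. Its intercurrent-event rule is "Subjects will be considered as non-responders for visits after ICEs".

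**Comparison.** Protocol Section 7.4: "pairwise comparison will be made between each ABBV-154 dose and placebo using the Cochran-Mantel-Haenszel (CMH) test, adjusting for stratification factors". SAP Section 9.2.2: "Using the Cochran-Mantel-Haenszel (CMH) model adjusted by stratification factors", and the factors named there are Baseline glucocorticoid dose (≥ 10 or < 10 mg/day) and length of prior treatment (≤ 1 or > 1 year). SAP Section 9.5 carries this over: "Additional efficacy endpoints described in Section 3.3 will be analyzed at all visits assessed using the same methods listed in above and Section 9.2".

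**Where Baseline is used.** For binary endpoints, Baseline appears only in the imputation model for data missing because of COVID-19, whose variable list includes "Baseline, and measurements at each visit". For continuous endpoints, the MMRM has the baseline measurement as a covariate. Change in hsCRP and in PMR-AS are both listed endpoints; change in ESR is not.

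**Population.** Protocol Section 5.1, criterion 9: "Subject must not exhibit clinical signs and symptoms of PMR" in the two weeks before Baseline. Criterion 23 requires stable prednisone of 5 to 15 mg/day. The laboratory entry criteria set no limit on ESR or hsCRP. SAP Section 7.1 tabulates Baseline PMR-AS in bands cut at 1.5, 7 and 17, so it provides for subjects on both sides of both PMR-AS thresholds.

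**The concern.** Symptom-free subjects on stable glucocorticoid are likely to be a mix of those who already meet a target and those who do not. Meeting the target later probably depends on where the subject started. The plan treats Baseline as prognostic in the MMRM for hsCRP and PMR-AS but leaves it out of the binary comparison of the same markers.

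Three things follow. With 40 subjects per arm, chance differences in Baseline status pass into the estimated difference. The interval is wider than the collected data require. And the binary and continuous results for one marker may disagree partly because only one of them is adjusted. All three dose comparisons share one placebo arm, so a placebo arm that happens to be unusual at Baseline moves all three differences in the same direction.

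**Working it through.** **1. The plan's own figure.** The only power statement concerns the primary endpoint: 37 flares, hazard ratio 0.296, two-sided 0.1, power above 90%.
- Hazard ratio: ln 0.70 / ln 0.30 = 0.296.
- Schoenfeld: √(37/4) × |ln 0.296| − 1.645 = 2.06, power 98.0%. Freedman's formula gives 95.1%.

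The statement is correct. No power figure is given for the threshold endpoints.

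**2. Inputs for the check**
- 40 per arm, from the sample size section.
- Share without rescue at Week 24, from the planned 30% and 70% flare-free at Week 36, assuming a constant hazard: 0.30^(24/36) = 0.448 on placebo and 0.70^(24/36) = 0.788 on the highest dose. The mean is 0.618. Rescue counts as non-response.
- *Assumed, because the documents give neither:* the share *a* not meeting the target at Baseline, and the chance of meeting it at Week 24 without rescue for those who did (*p*) and did not (*q*) meet it at Baseline.

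**3. Formulas**
- SD of chance imbalance = √(2a(1 − a)/40).
- Slope *s* (movement of the estimate per point of imbalance) = (p − q) × 0.618.
- Variance without Baseline: V = [p₁(1 − p₁) + p₀(1 − p₀)]/40, where p₁ and p₀ are the overall achievement rates.
- Variance ratio, planned to adjusted ≈ V / [V − 2a(1 − a)s²/40].

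Central case (a = 25%, p = 90%, q = 35%):
- Rate without rescue: 0.75 × 0.90 + 0.25 × 0.35 = 0.7625. So p₀ = 0.448 × 0.7625 = 0.342 and p₁ = 0.788 × 0.7625 = 0.601.
- V = (0.2249 + 0.2398)/40 = 0.01162, an SD of 10.8 points.
- s = 0.55 × 0.618 = 0.34.
- Ratio = 0.01162 / (0.01162 − 0.375 × 0.340²/40) = 0.01162/0.01053 = 1.10.

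| Dependence | a | p / q | Imbalance SD (points) | Slope | Shift per SD (points) | Ratio, formula | Ratio, 8-stratum CMH, simulated |
|---|---|---|---|---|---|---|---|
| Weak | 15% | 90% / 60% | 8.0 | 0.19 | 1.5 | 1.02 | 0.97 |
| Central | 25% | 90% / 35% | 9.7 | 0.34 | 3.3 | 1.10 | 1.01 to 1.05 |
| Strong | 35% | 95% / 20% | 10.7 | 0.46 | 4.9 | 1.27 | 1.20 |

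**4. Simulation, regression against the planned four-stratum CMH.** A model with treatment, the two stratification factors and Baseline status gave variance ratios of 1.03 to 1.28. The planned estimate had a slope of 0.19 to 0.47 on the imbalance; the regression estimate had a slope of about 0. Both ranges agree with the formulas.

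**5. Simulation, Baseline status as a third CMH factor.** This makes 8 strata for 80 subjects. A stratum with subjects in only one arm drops out of the Mantel-Haenszel estimate. That happened in about half of central-case trials, in about 79% at a = 15% and in about 91% at a = 10%. The last column of the table shows the result.

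**6. Level and a wider grid.** A second simulation varied the share meeting the target at Baseline from 30% to 85%, with placebo achievement of 50%/30%, 60%/20% or 70%/10% by Baseline status. The planned test rejected a true null in 9.4% to 11.2% of trials, against a nominal 10%. The shift per SD of imbalance was 1.6 to 6.7 points.

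**The case against.** Stratifying only by the randomisation factors is a standard choice, and randomisation makes the comparison unbiased on average. The shift is already contained in the standard error: 3.3 points against an SD of 10.8 is 0.31 of a standard error in the central case. Every input that drives the gain is assumed. The endpoints rank below the primary and secondary ones, carry no power claim and sit in a Phase 2 study without overall type I error control. Baseline hsCRP, ESR and PMR-AS will be summarised by arm, so an imbalance would be seen, and the MMRM covers hsCRP and PMR-AS on the continuous scale.

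All of this stands, and it keeps the point minor. It does not remove it. ESR has no adjusted counterpart. Seeing an imbalance without a prespecified adjustment leaves only a post hoc explanation.

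Three stronger readings are tempting, and the documents do not support them:
- *A subject normal at Baseline is an automatic achiever.* The subject must still meet the threshold at the visit, and any visit after rescue, an immunomodulator or a glucocorticoid violation counts as non-response.
- *The analysis is biased or its error rate is inflated.* It is neither; the simulated level stays near 10%.
- *Subjects already at target should be excluded.* In a taper trial, keeping control is a legitimate outcome, and the ITT Population should stay whole.

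**Conclusion.** The point holds as a missed refinement. The binary comparison ignores a Baseline value that is already collected and that the plan uses for the continuous versions of hsCRP and PMR-AS.

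The estimated difference shifts by about 2 to 5 points per SD of chance imbalance. Regression adjustment is worth a variance ratio of 1.03 to 1.28. That is a variance reduction of 3% (1 − 1/1.03) to 22% (1 − 1/1.28), or about 1 (40 × 0.03) to 11 (40 × 0.28) extra subjects per arm.

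These figures assume that 15% to 35% of subjects miss the target at Baseline, the listed dependence on Baseline, constant hazards, and stratification factors that are not themselves prognostic. If dependence on Baseline is weak, the gain is close to nothing. No primary or secondary conclusion is affected.

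**What to change.** In SAP Sections 9.2.2 and 9.5, state that ESR ≤ 30 mm/h, hsCRP ≤ ULN, PMR-AS < 1.5 and PMR-AS < 7 will be analysed by a regression model, for example logistic regression reported as a standardised risk difference. Include treatment, the two stratification factors and the Baseline value (or Baseline status). Keep the full ITT Population and the existing intercurrent-event and missing-data rules, and combine the risk differences over the imputed datasets as already planned. Tabulate achievement by Baseline status and arm.

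Do not add Baseline status as a third CMH factor: with 8 strata the gain is near zero or slightly negative unless dependence on Baseline is strong.

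The cost is a sentence or two in the SAP and one table, with no new data. The downside is that a model-based estimate replaces the CMH for these endpoints, so the SAP should name a fallback for non-convergence. The change should be made before unblinded results for these endpoints are seen.

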3.5 Safety Measures

1. Treatment-emergent adverse events (TEAEs), serious adverse events (SAEs), and AEs leading to discontinuation of study drug;
2. Occurrence of potentially glucocorticoid-related AEs; and
3. Potentially clinically significant laboratory, vital signs, and electrocardiogram (ECG) variables.

3.6 Pharmacokinetic and Immunogenicity Endpoints

Serum or plasma concentrations of the conjugated ADC, total antibody, free payload A-1677770 will be determined at baseline (predose) and at timepoints during the treatment period as specified in the Activity Schedule ([Appendix F](#)).

Development of anti-drug antibody (ADA) to ABBV-154 will be evaluated and if confirmed positive, titers will be measured. Samples that are confirmed positive may be further characterized in a validated neutralizing antibody (nAb) assay. Immunogenicity samples will be collected at baseline (predose) and at timepoints as specified in the Activity Schedule ([Appendix F](#)).

In addition, optional PK samples will be collected from approximately 32 subjects (approximately 8 subjects in each arm) who consent to participate in the optional PK sampling to provide additional data for PK characterization following repeated administrations. For these subjects, in addition to the standard sampling schedule, blood samples will also be collected at the following time points: Days 3, 4, 87, 88, 92 (Week 13) and 99 (Week 14).

3.7 Biomarker Research Endpoints

The effect of the ADC compound on glucocorticoid-related endpoints will be assessed by blood samples collected at specified time points (Activity Schedule, [Appendix F](#)) throughout the study. The biomarkers to be analyzed include, but are not limited to:

- [REDACTED]
- [REDACTED]

Provision of these biospecimens for biomarker research is mandatory, but they will not be collected from sites where local regulations do not allow for the collection, use, and storage of samples described in the protocol.

Additional optional biospecimens (whole blood for serum, plasma, peripheral blood mononuclear cells, ribonucleic acid [RNA], and deoxyribonucleic acid [DNA]) will be collected at specified time points (Activity Schedule, [Appendix F](#)) throughout the study to evaluate known and/or novel disease-related or drug-related biomarkers in circulation or at tissue sites. Types of biomarkers may include nucleic acids, proteins, cell populations, lipids, and/or metabolites, either free or in association with particular cell

4 INVESTIGATIONAL PLAN

4.1 Overall Study Design and Plan

Study M20-370 is a randomized, double-blind, placebo-controlled, multicenter, 52-week Phase 2 study to assess the safety, tolerability, efficacy, PK, PD, and immunogenicity following multiple subcutaneous (SC) injections of ABBV-154 or placebo in 160 subjects with glucocorticoid-dependent PMR, as defined in Section 5.1.

The Screening Period may be up to 35 days. At the Baseline Visit, subjects will be randomized to one of 4 treatment arms in a 1:1:1:1 ratio, as follows: placebo administered SC in combination with a glucocorticoid taper or ABBV-154 administered as 40 mg every other week (EOW), 150 mg EOW, or 340 mg EOW in combination with a glucocorticoid taper. The glucocorticoid taper is identical for placebo and active treatment groups. Starting at Baseline, each subject will switch from oral glucocorticoids obtained from independent sources to oral prednisone/prednisolone provided by the Sponsor at the equivalent dose that the subject was taking just prior to the Baseline Visit, rounded up to the nearest 1 mg to a maximum of 15 mg. Beginning at Week 3, subjects will taper prednisone/prednisolone per the protocol-defined glucocorticoid taper schedule to 0 mg by Week 24 and remain off prednisone/prednisolone until the end of the Treatment Period, Week 52, unless a PMR flare is confirmed. A safety follow-up visit will be performed approximately 70 days after the last administration of ABBV-154/placebo.

If a subject has a suspected PMR flare at any time during the study, the flare should be confirmed according to the protocol-defined flare definition as soon as possible, prior to initiating glucocorticoid rescue treatment. Flare may be confirmed at either a scheduled visit or unscheduled visit. PMR must be confirmed as the cause of flare by eliminating other causes of the subject's symptoms/signs such as infection or other underlying disease. Once flare is confirmed at the visit, glucocorticoid rescue can be administered with the dose and subsequent tapering at the discretion of the investigator, taking into consideration local standard of care, the subject's preflare and/or baseline dose, and not exceeding 15 mg/day.

Addition of immunomodulators other than glucocorticoid rescue, as outlined above, are not permitted for rescue. If the investigator determines it is in the best interest of the subject to start an immunomodulator, the subject must discontinue study drug (ABBV-154/placebo and Sponsor-supplied prednisone/prednisolone; glucocorticoid will then be prescribed by the investigator as necessary, with dosing based on the investigator's judgement and in accordance with local standard of care).

The Primary Analysis will be performed after all subjects have either completed the Week 24 visit or withdrawn from the study. Interim analyses may be performed to reassess the treatment regimens in this study and to inform development of future studies.

[figure not shown]
A final analysis will be conducted after all subjects have either withdrawn from the study or completed Week 52 and the safety Follow-up Visit. To maintain integrity of the trial, the study sites and subjects will remain blinded until the final analysis is completed. Selected AbbVie personnel may be unblinded to treatment assignment to conduct interim analyses or after an interim analysis to support regulatory interaction; details will be included in the interim unblinding plan (IUP).

Subjects in select countries and sites where the digital health technology device is deployed and available may also participate in a Wearable Device Substudy. Subjects participating in this substudy will wear a watch-like digital device on the wrist that will collect data reflecting the subject's UL-ROM and daily activity and sleep parameters (see Section 3.9 of the Operations Manual [Appendix H]). Enrollment will be capped at 96 subjects.

There will be optional serial photography for subjects who consent and at sites where photography is available.

The schematic of the study is shown in Figure 1. Further details regarding study procedures are located in the Operations Manual (Appendix H). See Section 5.1 for information regarding eligibility criteria.

Figure 1. Study Schematic

EOW = every other week; PMR = polymyalgia rheumatica; SC = subcutaneous

